### **11.6. Physical Exam**

Physical exam data for each participant will also be presented in a listing.

## **12. IDENTIFICATION AND SUMMARY OF PROTOCOL DEVIATIONS**

Important major protocol deviations, such as entry criteria violation and significant treatment non-compliance will be summarized as far as they can be extracted from numeric or coded study data.

### **13. DATA QUALITY ASSURANCE**

Accurate and reliable data collection will be ensured by verification and cross check of the CRFs against the investigator's records by the study monitor (source document verification) and by the maintenance of a drug-dispensing log by the investigator. Collected data will be entered into a computer database and subject to electronic and manual quality assurance procedures.

## APPENDIX 1. IMPUTATION ALGORITHM FOR PARTIAL AND MISSING DATES

This section describes missing date imputation methods.

### For Adverse Events

If onset date is completely missing, onset date is set to date of first dose.

If (year is present and month and day are missing) or (year and day are present and month is missing):

- If year = year of first dose, then set month and day to month and day of first dose
- If year < year of first dose, then set month and day to December 31.
- If year > year of first dose, then set month and day to January 1.

If month and year are present and day is missing:

- If year = year of first dose and
  - If month = month of first dose then set day to day of first dose
  - If month < month of first dose then set day to last day of month
  - If month > month of first dose then set day to first day of month
- If year < year of first dose then set day to last day of month
- If year > year of first dose then set day to first day of month

For all other cases, set onset date to date of first dose.

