## 11. SAFETY ANALYSES

Safety analyses will be performed on the Safety Population. Safety evaluations will be based on the incidence and severity of adverse events, as well as on ECG measurements, vital signs and Columbia Suicide Severity Rating Scale (C-SSRS). Safety variables will be tabulated and presented by study drug actually received.

In this crossover study, AEs will be attributed to the last treatment the participant received prior to the AEs.

Because there is no pre-specified safety outcome defined in terms of AEs or vital signs, any formal comparisons between the treatment arms with respect to specific safety parameters will be post-hoc.

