### 11.2. Adverse Events

Each AE and SAE term will be recorded as a verbatim term on the case report forms (CRFs). All AEs and SAEs will be coded by primary System Organ Class (SOC) and mapped to a preferred term using the MedDRA Version 24.0. The investigator will assess AE severity and relationship to the study treatment.

All AEs will be listed. However, only treatment emergent adverse events (TEAEs) will be included in the AE summaries. A TEAE is defined as any AE with an onset date in the interval between the first study treatment dosing date and 7 days after the last study treatment dosing date. In addition, any AEs that the investigators deem to be treatment related will also be considered TEAEs and will be included in the AE summaries.

For the purpose of calculating treatment emergence and inclusion in summary tables, incomplete onset dates will be imputed using the method described in Appendix A.

AEs will be summarized by the number and percentage of participants in each primary SOC and preferred term. Participants will be counted only once for each primary SOC and each preferred term. Summary tables of AEs by primary SOC, preferred term and severity will be provided. If a participant has more than one AE coded to the same preferred term, the participant will be counted only once for that preferred term by using the event with the highest severity. Similarly, if a participant has more than one AE within a primary SOC category, the participant will be counted only once in that SOC category by using the event with the highest severity. AEs by

primary SOC, preferred term and relationship to study drug will be provided as well. If a participant has more than one AE coded to the same preferred term, the participant will be counted only once for that preferred term by using the most related event. Similarly, if a participant has more than one AE within a primary SOC category, the participant will be counted only once in that primary SOC category by using the most related event. In addition, serious adverse events (SAEs) by primary SOC and preferred term will be provided. Deaths and SAEs will be summarized similarly to AEs. All adverse event tables will also include the total number of events, counting multiple events per participant.

In the AE summary, preferred terms within each SOC will appear in descending frequency order within each active treatment group.

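### Incomplete AE onset dates are imputed from the first dose of the study, so most such Period 2 events are counted under the Period 1 treatment

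*SAP*

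**What the plan says.** SAP Appendix 1 (For Adverse Events) works out every incomplete onset relative to one date, the first dose.

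- Nothing known: "If onset date is completely missing, onset date is set to date of first dose". A year-only onset in the year of first dose, and any case not otherwise covered, gets the same date.
- Day missing, same year: "If month = month of first dose then set day to day of first dose", but "If month > month of first dose then set day to first day of month".
- Later year: 1 January, or the 1st of the month if the month is known.

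The AE rule mentions neither period nor crossover.

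SAP 11.2 states the use of these dates: "For the purpose of calculating treatment emergence and inclusion in summary tables, incomplete onset dates will be imputed". A TEAE needs an "onset date in the interval between the first study treatment dosing date and 7 days after the last study treatment dosing date", which is one window across the whole study. SAP 11 adds that "AEs will be attributed to the last treatment the participant received prior to the AEs" and that "Safety variables will be tabulated and presented by study drug actually received". The SAP gives no other rule for placing an incompletely dated event in a period.

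**The concern.** An early anchor is reasonable for deciding whether an event is treatment-emergent, because it keeps doubtful events in the tables. In a crossover the onset date has a second job: it decides which treatment the event belongs to. The Appendix 1 rule was not adapted to that.

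The imputed date is never later than the true on-study onset, so the error runs one way in time, from Period 2 back to the Period 1 treatment. In the solriamfetol-first sequence, placebo events move to solriamfetol. In the placebo-first sequence, solriamfetol events move to placebo. The two treatments' rates are drawn together, and a real excess on either one is understated. TEAE incidence and severity is a listed safety endpoint (SAP 4.1). A single misplaced serious or rare event can also matter by itself.

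**Working it through.** **Inputs**
- Period 1 starts the day after randomization, so first dose is Day 1 (Protocol 4.1.3).
- First Period 2 dose is on Day 21 to 24 (Protocol Table 3, SAP Table 2).
- Washout is 1 week (Protocol 4.1.4).
- The TEAE window runs to 7 days after last dose (SAP 11.2).
- Sequences are 1:1 (SAP 4.3.2).
- Assumed, not in the documents: onset uniform over the days considered, and the share of incomplete dates.

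The plan states no figure on this point to reproduce.

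**Two illustrations**
- First dose 2 March, first Period 2 dose 23 March (Day 22). An event starting 26 March and recorded as March is dated 2 March, so it goes to the Period 1 treatment.
- First dose 20 March, first Period 2 dose 10 April (Day 22). An event starting 14 April and recorded as April is dated 1 April (Day 13), so it also goes to the Period 1 treatment.

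**Step 1: share misassigned (m).** The rule was applied to 1,461 randomization dates (a 4-year cycle), each with the first Period 2 dose on Day 21, 22, 23 and 24 and with every onset day. An event is misassigned if its imputed date falls before the first Period 2 dose.

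| Known parts | Onset over 14 + 7 days | Onset over 14 dosing days |
|---|---|---|
| None | 100% | 100% |
| Year | 97.0% | 97.9% |
| Month and year | 63.9% | 75.4% |

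Period 1 or washout events moved into Period 2: 0%.

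**Step 2: effect on the treatment difference.** Let f be the share of Period 2 AE dates that are incomplete. Let s1, s2 be the solriamfetol and p1, p2 the placebo event rates in Periods 1 and 2, with equal sequences.

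- Solriamfetol total = s1 + s2(1 − fm) + p2·fm
- Placebo total = p1 + p2(1 − fm) + s2·fm
- Difference = (s1 − p1) + (s2 − p2)(1 − 2fm)

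If the treatment difference is the same in both periods, this is the true difference × (1 − fm). For an assumed true difference of 20 points:

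| f (assumed) | m = 0.64 | m = 1 |
|---|---|---|
| 1% | 20 × (1 − 0.0064) = 19.9 | 20 × 0.99 = 19.8 |
| 5% | 20 × (1 − 0.032) = 19.4 | 20 × 0.95 = 19.0 |
| 10% | 20 × (1 − 0.064) = 18.7 | 20 × 0.90 = 18.0 |

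**Step 3: would a Period 2 default do better?** Take all incompletely dated events that start after Visit 5, spread over 7 washout and 21 Period 2 days, with no end date available. At present only Period 2 events are wrong (21/28 = 75% of the total, times m). With ambiguous events placed in Period 2, only washout events are wrong (7/28 = 25%, times the share of them that is ambiguous).

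| Known parts | Wrong now | Washout events moved to Period 2 | Wrong after |
|---|---|---|---|
| None | 0.75 × 100% = 75.0% | 100% | 25.0% |
| Year | 0.75 × 97.0% = 72.7% | 99% | 24.7% |
| Month and year | 0.75 × 63.9% = 47.9% | 87% | 21.7% |

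Without the 7-day tail (7 washout + 14 Period 2 days) the error still falls: from 66.7%, 65.3% and 50.2% to 33.3%, 33.0% and 29.0%.

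**The case against.** The strongest reply is about reading. SAP 11.2 introduces imputation for treatment emergence and table inclusion, and the attribution rule in SAP 11 does not mention imputed dates. Appendix 1 does not say which first dose it means, and the schedule uses the term for Period 2 as well. On this view the SAP is silent on attribution and does not prescribe the wrong one.

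This does not hold. The tables in question are split by treatment, attribution needs a date, and the imputed date is the only one supplied. The anchor is also settled in practice. The concomitant-medication part of Appendix 1 uses the same term to separate prior from concomitant drugs, and SAP 9 ties that split to the first administration of any study treatment. If a period-specific dose was meant, the period would have to be known first, and no rule provides it.

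The second reply is about size, and most of it stands. AEs are collected at Visits 5, 8 and 9 of a short study, CRFs are checked against source (SAP 13), all AEs are listed, and no formal safety testing is planned (Protocol 9.4.5). Incomplete dates are probably few.

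Three smaller points also stand. The documents do not confirm that the CRF keeps the visit of first record. A Period 2 default misplaces most incompletely dated washout events. The Appendix A reference is a clerical slip that adds no weight.

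**Conclusion.** The concern holds. Followed as written, the SAP counts 64% to 100% of incompletely dated Period 2 events under the Period 1 treatment, depending on which date parts are known, with no error in the other direction. These shares assume uniform onset and the whole-study reading of first dose.

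The effect on the by-treatment TEAE tables is likely modest: a loss of 0.1 to 2.0 points from an assumed 20-point difference when 1% to 10% of dates are incomplete. That range is an assumption. The dilution formula also needs equal sequences and the same treatment difference in both periods. The primary endpoint is not affected. The correction should be made before database lock because it is cheap and the bias always runs towards no difference.

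**What to change.** In SAP Appendix 1, bound the imputed AE onset by the known date parts, the AE end date, the visit at which the event was first recorded, and the actual dosing dates of each period:

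1. Events first recorded by Visit 5 stay in Period 1.
2. For events first recorded after Visit 5 whose known parts are compatible with Period 2, use the first Period 2 dose date in place of the study's first dose or the 1st of the month. If the known parts or the end date put onset before that dose, keep the Period 1 treatment, as SAP 11 requires for washout events.
3. Participants who never started Period 2, including those seen at an early-discontinuation Visit 9, stay with the Period 1 treatment.
4. Where washout and Period 2 cannot be told apart, pre-specify one default, flag the events, and repeat the TEAE table under the other attribution.

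SAP 11.2 says "incomplete onset dates will be imputed using the method described in Appendix A"; change this to Appendix 1.

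The cost is a few lines of text and programming and one sensitivity table. No new data collection is needed, provided the CRF identifies the visit at which each AE was first recorded; confirm this first. With Period 2 as the default, 87% to 100% of incompletely dated washout events without an end date would move to Period 2. Total misattribution still falls, and end dates reduce what remains.

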### For Concomitant Medications

Start Date: If start date is completely missing and end date is not prior to date of first dose, then the medication will be classified as concomitant. If start date is completely missing and end date is prior to date of first dose, then the medication will be classified as prior.

If (year is present and month and day are missing) or (year and day are present and month is missing) then set month and day to January 1. If year and month are present and day is missing then set day to first day of month.

End Date: If end date is completely missing then the medication will be classified as concomitant.

If (year is present and month and day are missing) or (year and day are present and month is missing) then set month and day to December 31. If year and month are present and day is missing then set day to last day of the month.

Note: that if both start and end dates are missing then the medication will be classified as concomitant.
